#### 4.2. Volunteers

#### 4.2.1. Sample size

A baseline versus 5-weeks post-treatment reduction of -9.2 (SD = 5.6) on the QIDS was observed in our recent pilot study. To inform what can be expected with 1mg psilocybin, we can refer to the recent end-of-life anxiety trial of Griffiths et al. [66] in which the reduction in scores on another standard scale (BDI) seen with the control condition (1-3mg/ 70kg psilocybin) was 50% that of the active condition, i.e. a reduction of 10.7 (22-30mg/70kg, active) versus 5.5 (1-3mg/70kg, control) at 5-weeks post-treatment. If 1mg psilocybin is equally as effective as the 1-3mg/70kg in the Griffiths study, i.e. 50% of the active dose (which is a conservative prediction, given that the difference in doses is greater, and the time since treatment is shorter), we can expect a mean reduction in QIDS scores of 9.2/2 = 4.7 points for

the 1mg condition. If we assume equal variance for both conditions, we would require 20 patients per condition to achieve the desired power of 80%, p < 0.05. We therefore propose to recruit a minimum of 30 patients per condition (60 completers in total for the RCT). These are appropriate numbers for the imaging, given that significant baseline v one-day post-treatment effects are being observed in BOLD resting-state functional connectivity, amygdala activations to emotional faces and CBF with just 15 patients in my recent pilot study (papers in preparation). Significant fMRI findings have been reported with escitalopram in similar paradigms and with similar sample sizes [67]. Equivalent efficacy (primary outcome) is predicted for the escitalopram vs 25mg psilocybin conditions but with different mechanisms of action. For example, we predict greater improvements in wellbeing (WEMWBS) with 25mg psilocybin vs escitalopram at 6-weeks post dosing day 1.

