#### 2. Project outline

#### 2. Main study design

This will be a two-*arm*, active comparator, *double-blind*, *randomized controlled*, betweensubjects, design in up to *60 completing* patients meeting DSM-IV criteria for *major depression* of a moderate to severe degree (17+ on the 21-item Hamilton Depression Rating Scale, HAM-D). The patients will be randomly allocated to two groups. Groups will receive either: 1) two on-site dosing sessions with 25mg p.o. psilocybin, 3 weeks apart, the first dosing session being followed by 6 weeks of daily inert placebo ingestion, 2) two dosing sessions with 1mg psilocybin (to our knowledge, sub-psychoactive), 3 weeks apart, the first dosing session being followed by 6 weeks of daily escitalopram (10 mg for the first 3 weeks then increasing to 20 mg for 3 weeks, in line with prescribing guidelines [79] and similar to previous literature [98]). See Figure 1 for details.

Condition one is the main experimental condition and condition 2 is a control condition. Condition 2 involves 6-weeks of treatment with a gold-standard antidepressant, escitalopram, adding an important comparative efficacy component to this trial. Both groups will receive equal preparation and follow-up before and after the dosing session. The blind is broken after 6 weeks, after which normal treatment ensues.

**Figure 1. Basic design.** Active components are highlighted in red. Please note, the psilocybin 'dosing sessions' are variously called 'dosing days' in what follows

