#### 2.1. Dose

## 2.1.1. Psilocybin

Patients in condition 1 will receive two doses of 25mg, 3 weeks apart from each other. In our recent open label feasibility study, this dose was well tolerated by all of the patients; no serious or unexpected adverse events occurred, and the mean patient rating of intensity of drug effects

was 7.5 (+2.5) out of 10, which was what we had planned to achieve. Based on these observations we feel confident that this dose maximises the potential for therapeutic benefit, whilst minimising the risk of acute adverse events. This view has been further supported by our conversations with other researchers working with psilocybin, such as those at Johns Hopkins University.

Regarding the control group, 1mg psilocybin has been chosen because evidence indicates it is pharmacologically 'inert' and yet capable of serving as an effective placebo [4], producing effects via expectancy alone, to a similar degree as a non-active placebo. Positive expectation is the major psychological factor underlying the 'placebo' effect, so the merit of using psilocybin in both conditions is that study staff and patients can be briefed to expect psilocybin in all conditions. Patients and therapy staff will be encouraged to expect and prepare for up to 25mg of psilocybin; thus, standardizing preparation and expectations prior to the dosing session.

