## 2.1.2. Escitalopram

Escitalopram is a highly selective serotonin reuptake inhibitor (SSRI) that was licensed in the US in 2002 as an approved treatment for major depressive disorder. It has since been prescribed to millions of people worldwide, becoming a gold-standard medication for depression. Meta-analyses have indicated that escitalopram is one of the best performing SSRIs in terms of tolerability and efficacy [77] and it is one of the most selective SSRIs [78].

Patients in condition 2 who receive an inactive dose of psilocybin (1mg) during the first dosing day, will subsequently receive 6 weeks of daily escitalopram. For the first 3 weeks they will receive 10mg-daily (1 capsule per day). After 3 weeks they will have a second 1mg psilocybin dosing day (without interrupting the daily escitalopram dosing schedule). After this, they will subsequently take 20mg of escitalopram daily (2 capsules per day) for three further weeks. The dose of 20mg is the recommended maximum dose for this commonly prescribed primary treatment for depression, and thus we would expect the patient's symptoms of depression to decrease. It would be expected that patients starting a course of SSRIs would report some improvements in depressive symptoms after even this relatively brief treatment period of 6 weeks [80, 81].

The dose of escitalopram can be lowered to 10mg from 20mg if patients appear not to be tolerating 20mg and ask to lower the dose or withdraw from the trial. This would be simple to implement as we would just instruct patients to take 1 capsule daily instead of 2. If, when the blind is broken at the 6 week endpoint, it transpires that the patient was actually in condition 1 and not in fact in the escitalopram condition, this would be logged.

We will be monitoring patients' response to escitalopram via weekly self-report measures, and measures of side effects. FDA guidelines report the following possible side-effects with escitalopram: headaches, dizziness, nausea, insomnia, dry mouth, impotence, decreased appetite, weight gain, vomiting, vivid dreams and a tingling sensation in arms, hands, feet and legs [79]. Insomnia and diarrhea are the most common side-effects, affecting 15% of individuals at 20mg [79].

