#### 4.1.2. Primary efficacy outcome measure and endpoint

Change in QIDS score from baseline (screening) to 6 weeks post initial dosing session (primary endpoint). Change after psilocybin (condition 1) vs change after escitalopram (condition 2). The criteria for determining response will be a reduction of 50% in the QIDS scores and remission will be scores of  $\leq 5$  on the QIDS, as per convention [12].

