## 10. Analysis

The data collected from this study will be used to gather new information and inform future studies. Data will be tabulated and descriptive parameters derived. The study is powered for a baseline vs week 6 t-test on the QIDS-16 (condition 1 vs condition 2) and this is the primary efficacy outcome and endpoint.

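### The sample size is worked out against 1 mg psilocybin alone, but the control arm also receives escitalopram, so the claim of power for the primary efficacy contrast is unsupported; superiority and equivalence are both stated as the expectation

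*Protocol*

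**What the plan says.** The sample size paragraph (Protocol 4.2.1) starts from the sponsor's pilot study: a QIDS reduction of 9.2 points, SD 5.6, at five weeks. For the control arm it says "To inform what can be expected with 1mg psilocybin, we can refer to the recent end-of-life anxiety trial". In that trial the low-dose psilocybin arm fell by 5.5 BDI points and the high-dose arm by 10.7. From this ratio of about one half it takes 4.7 QIDS points for 1 mg and describes the step as one "which is a conservative prediction, given that the difference in doses is greater". With equal variances it concludes that "we would require 20 patients per condition to achieve the desired power of 80%, p < 0.05", and it plans 30 per condition (60 completers).

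The comparator is described differently elsewhere. Section 2 (Main study design) says "Condition 2 involves 6-weeks of treatment with a gold-standard antidepressant, escitalopram, adding an important comparative efficacy component to this trial". Section 4.1.2 defines the primary efficacy contrast as "Change after psilocybin (condition 1) vs change after escitalopram (condition 2". Section 10 says "The study is powered for a baseline vs week 6 t-test on the QIDS-16 (condition 1 vs condition 2".

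On the two components of condition 2, section 2.1.1 describes 1 mg psilocybin as "producing effects via expectancy alone, to a similar degree as a non-active placebo", and section 2.1.2 expects that "patients starting a course of SSRIs would report some improvements in depressive symptoms after even this relatively brief treatment period of 6 weeks".

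On the hypothesis, section 1.1 (Basic study design) makes superior efficacy over escitalopram, together with a different mechanism, the main purpose, and comparable efficacy a secondary prediction. Section 4.2.1 predicts equivalent efficacy on the primary outcome and gives no margin.

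**The concern.** The planned difference is one between a full dose of psilocybin and a placebo-like control. The trial contains no such control arm. The reasons given for calling the control assumption conservative (a larger dose gap and different timing) concern psilocybin only. Any benefit that escitalopram adds to the 1 mg response works the other way, because it narrows the difference that the trial has to detect.

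A reader who takes sections 4.2.1 and 10 together will believe that the trial has at least 80% power for psilocybin versus escitalopram. If the result is not significant, that reader could call it a well-powered failure of superiority. Another reader, relying on the equivalence sentence in 4.2.1, could call the same result confirmation of what was predicted. The calculation shown supports neither reading.

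**Working it through.** **Inputs.** From section 4.2.1: psilocybin reduction 9.2, SD 5.6 in both arms, control reduction 4.7 as printed, power 80%, alpha 0.05, 20 per arm required, 30 per arm planned. Sidedness is not stated. The protocol gives no QIDS change for escitalopram and no equivalence margin.

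**Method.** Two-sample t-test with equal arms. Power comes from the noncentral t distribution with 2n − 2 degrees of freedom and noncentrality δ / (SD × √(2/n)).

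**1. The control figure.** 9.2 / 2 = 4.6, not 4.7. The printed 4.7 follows from the BDI ratio: 9.2 × 5.5 / 10.7 = 4.73. The planned difference is therefore 4.5 to 4.6 points.

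**2. Reproducing the stated 20 per arm (SD 5.6).**

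| Difference | n per arm, one-sided 5% | n per arm, two-sided 5% | Power at n = 20, one-sided / two-sided |
|---|---|---|---|
| 4.6 | 20 | 25 | 82% / 72% |
| 4.5 | 20 | 26 | 80% / 70% |

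The figure of 20 reproduces only for a one-sided test. The planned 30 covers both readings: for 4.5 to 4.6 points its power is 86% to 88% two-sided and 92% to 93% one-sided.

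**3. What 30 per arm can detect.** The standard error of the difference is 5.6 × √(2/30) = 1.446. The true difference needed for 80% power is:

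| SD | Two-sided 5% | One-sided 5% |
|---|---|---|
| 5 (assumed) | 3.68 | 3.25 |
| 5.6 (protocol) | 4.12 | 3.64 |
| 6 (assumed) | 4.41 | 3.90 |
| 7 (assumed) | 5.15 | 4.55 |

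**4. How much the escitalopram arm may improve.** With psilocybin at 9.2 and SD 5.6, the ceiling is 9.2 − 4.12 = 5.08 points two-sided, or 9.2 − 3.64 = 5.56 one-sided. That is only 0.4 to 0.5 points (two-sided) or 0.9 to 1.0 points (one-sided) above the 4.6 to 4.7 assumed for 1 mg alone. If psilocybin achieves an assumed 8.2 or 10.2 instead, the ceiling becomes 4.1 or 6.1 two-sided, and 4.6 or 6.6 one-sided.

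**5. Power by improvement in the escitalopram arm** (psilocybin 9.2, SD 5.6, 30 per arm; the last three rows are assumptions):

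| Improvement | Difference | Two-sided | One-sided |
|---|---|---|---|
| 4.6 | 4.6 | 88% | 93% |
| 4.7 | 4.5 | 86% | 92% |
| 6 | 3.2 | 59% | 71% |
| 7 | 2.2 | 32% | 44% |
| 8 | 1.2 | 13% | 20% |

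**6. If efficacy is equal, as section 4.2.1 predicts.** The difference test in section 10 then rejects only at its 5% error rate. For an equivalence test (two one-sided tests at 5% each, true difference 0, normal approximation), 30 per arm gives 80% power only for a margin of at least 1.446 × (1.645 + 1.282) = 4.2 points. An assumed margin of 3 points would have 33% power.

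**The case against.** The strongest reply is that a calculation for condition 1 versus condition 2 does exist. Section 4.2.1 assigns the 4.7 points to the 1 mg condition, and in a two-arm trial that is condition 2. On this view the defect is a badly sourced control input, not a missing calculation. The assumed control response is also not zero but half the active one, section 2.1.2 promises only some improvement, and 30 per arm leaves room above 20. The low power figures rest on escitalopram responses that the protocol never states.

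Part of this stands. The sample size is adequate for the inputs as printed, and severe underpowering is possible rather than shown. But calling condition 2 the 1 mg condition does not bring escitalopram into the calculation, and the room above 20 does not establish power against a regimen whose expected response is never given.

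It is also fair to say that sidedness is often left to the SAP, that section 1.1 gives the fMRI endpoint and the mechanism great weight, and that equivalence is predicted rather than claimed as a test. The first makes sidedness a minor point here. The other two do not remove the contradiction between sections 1.1 and 4.2.1 on the primary efficacy outcome.

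**Conclusion.** The concern holds. Section 10's power claim is not supported for the contrast defined in section 4.1.2, because the only calculation shown omits the active drug in the control arm. Given the pilot's 9.2 and SD 5.6, power of 80% or more depends on the escitalopram arm improving by no more than about 5.1 points (two-sided) or 5.6 (one-sided), and the protocol gives no basis for assuming that. The 9.2 is itself uncertain: it comes from an uncontrolled pilot in treatment-resistant depression (sections 1.1 Background and 3), and section 2.4.1 says this trial is not restricted to that population.

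The hypothesis conflict is independent of these numbers: superiority as the main hypothesis and equivalence on the primary outcome cannot both govern one test. The unstated sidedness and the 9.2/2 slip are minor, since the planned 30 covers either. The point must be fixed because it concerns what the primary efficacy result can be said to show.

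**What to change.** In sections 4.2.1 and 10, replace the power claim with the detectable difference, after the sponsor has chosen the sidedness. For a two-sided test:

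> With 30 evaluable patients per arm, SD 5.6 and two-sided alpha 5%, the trial has 80% power for a true psilocybin–escitalopram difference of 4.1 points in QIDS change. Power for true differences of 4, 3, 2 and 1 points is 78%, 53%, 27% and 10%. The trial is not powered for smaller differences and was not sized to show equivalence.

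For a one-sided test the figures are 3.6 points, and 86%, 66%, 39% and 17%.

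Delete the derivation for 1 mg alone, or label it as not applying to this comparator. If it stays, write 9.2/2 = 4.6 or show 9.2 × 5.5/10.7 = 4.7. If the sponsor has a sourced expectation for QIDS change under the full condition 2 regimen, it can be stated and power recomputed from it.

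Make sections 1.1 and 4.2.1 name one primary efficacy hypothesis. The t-test in section 10 fits superiority; equivalence would need a stated margin and its own test.

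The cost is protocol wording and no extra patients. The stated power becomes conditional and less favourable, and the sponsor must commit to one hypothesis and one sidedness.

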## 1.1. Basic study design

The main experimental condition (**condition 1**) in this study will involve two high doses of 25mg psilocybin (per os, p.o.), 3 weeks apart. The first dose will be followed by 6 weeks of daily (inert) placebo capsule ingestion (condition 1, fig. 1). The control condition (**condition 2**) will involve two dosing sessions, also 3 weeks apart, with a presumed inactive dose of

psilocybin (1mg p.o.). The first dose will be followed by 6-weeks of daily escitalopram capsule ingestion (fig. 1).

Thus, there will be a dedicated on-site dosing day for both conditions (named here 'initial dosing session') followed by 6 weeks of daily capsule ingestion at home and a second dosing session 3 weeks after the first. The primary endpoint for assessing efficacy is 6 weeks after the initial dosing session, when the blind will be broken at the final study visit. Unblinded follow-up will occur for a further 6 months to assess safety and any potential enduring effects.

The main purpose of this design is to test the hypothesis that two doses of psilocybin, a design similar to what may be done in future therapy, will show a superior efficacy to escitalopram and crucially, a different *mechanism of action*. Secondarily, we predict that conditions 1 and 2 will show comparable efficacy at 6 weeks but with a different side-effect profile, e.g. we predict that changes in sexual dysfunction will be different across conditions and that psilocybin will act more rapidly to alleviate depressive symptoms.

Regarding the primary outcome, we will use functional magnetic resonance imaging (fMRI) at baseline and six weeks after the initial dosing session to identify how brain activity changes before and after two doses of 25mg psilocybin vs 6 weeks of daily escitalopram.

We predict that fMRI measured amygdala blood oxygen level dependent (BOLD) responses to emotional faces after-versus-before treatment will be greater in condition 1 (psilocybin) than in condition 2 (escitalopram).

This trial promises to significantly advance our knowledge of the safety, efficacy and mechanism of action of psilocybin for MDD by comparing it with a major conventional treatment for depression. The comparison with escitalopram adds an important component to this trial which may ultimately lead to the development of psilocybin as an alternative treatment option for patients with MDD.

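### Protocol 4.2.1: the printed 9.2/2 = 4.7 is false, and the stated 20 per condition for 80% power matches only a one-sided 5% test that the protocol never declares

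*Protocol*

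**What the plan says.** Section 4.2.1 (Sample size) takes its active-arm input from the pilot study: a "reduction of -9.2 (SD = 5.6) on the QIDS was observed in our recent pilot study". For 1mg psilocybin it borrows a ratio from a published end-of-life anxiety trial, where BDI fell by 10.7 with the active dose and 5.5 with the control dose. It calls this 50% and writes "we can expect a mean reduction in QIDS scores of 9.2/2 = 4.7 points". Assuming equal variance in both conditions, it concludes that "we would require 20 patients per condition to achieve the desired power of 80%, p < 0.05", and continues: "We therefore propose to recruit a minimum of 30 patients per condition", that is, 60 completers.

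Section 10 (Analysis) names the test: "The study is powered for a baseline vs week 6 t-test on the QIDS-16", condition 1 versus condition 2.

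No section says whether the test is one- or two-sided, and the stated hypotheses do not settle it. Section 1.1 says psilocybin "will show a superior efficacy to escitalopram", but adds as a secondary prediction that "we predict that conditions 1 and 2 will show comparable efficacy at 6 weeks". Section 4.2.1 itself states: "Equivalent efficacy (primary outcome) is predicted for the escitalopram vs 25mg psilocybin conditions".

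**The concern.** A sample-size statement should let a reader recover n from the difference, SD, power and significance level. This one does not, for two reasons.

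First, the equation that produces the control-arm input is false as printed, so the difference being powered for is uncertain: 4.5 from the printed value, 4.6 from the printed expression, 4.47 from the unrounded source ratio.

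Second, an unqualified p < 0.05 is ordinarily read as two-sided, and on that reading 20 per condition falls well short of 80% power. The protocol then bases its planned size on the 20 through the word therefore. At stake is whether the stated calculation is correct and reproducible. The planned number of patients does not depend on it.

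**Working it through.** **Inputs, all from section 4.2.1 unless noted.** Active reduction 9.2; SD 5.6 in both conditions; 80% power; significance level 0.05; equal allocation; two-sample t-test (section 10).

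**Control reduction and difference, three readings**
- As the expression is printed: 9.2/2 = 4.6; difference 9.2 − 4.6 = 4.6; d = 4.6/5.6 = 0.821.
- As the value is printed: 4.7; difference 9.2 − 4.7 = 4.5; d = 4.5/5.6 = 0.804.
- From the unrounded ratio: 5.5/10.7 = 0.514; 9.2 × 0.514 = 4.73; difference 4.47; d = 4.47/5.6 = 0.798.

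**Reproducing the stated 20.** The exact calculation for a two-sample t-test uses the noncentral t distribution with 2n − 2 degrees of freedom and noncentrality d × √(n/2).

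| Difference | Sides | n per condition for 80% | Power at 20 |
|---|---|---|---|
| 4.6 | one | 19.04, so 20 | 81.8% |
| 4.5 | one | 19.86, so 20 | 80.3% |
| 4.47 | one | 20.11, so 21 | 79.8% |
| 4.6 | two | 24.26, so 25 | 71.6% |
| 4.5 | two | 25.31, so 26 | 69.7% |
| 4.47 | two | 25.62, so 26 | 69.2% |

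The figure of 20 is reproduced one-sided at a difference of 4.5 or 4.6. It is not reproduced two-sided at any of the three differences.

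**Does the method explain the gap?** The normal approximation is n = 2 × (z for alpha + z for power)² × (SD/difference)².
- Two-sided: 2 × (1.960 + 0.842)² × (5.6/4.6)² = 23.3, so 24; with 4.5 it is 24.3, so 25.
- One-sided: 2 × (1.645 + 0.842)² × (5.6/4.6)² = 18.3, so 19; with 4.5 it is 19.1, so 20.

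The two-sided results still miss 20. A paired or one-sample t-test on the same inputs gives 11 to 15, which does not fit either.

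**Power at the candidate sizes, two-sided 5%**
- Difference 4.6: 81.2% at 25; 87.9% at 30.
- Difference 4.5: 79.5% at 25; 81.1% at 26; 86.4% at 30.
- Difference 4.47: 79.0% at 25; 80.6% at 26; 86.0% at 30.

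**Effect of the 4.7 slip alone.** Moving from 4.6 to 4.7 for the control reduction changes the two-sided n from 25 to 26 and leaves the one-sided n at 20.

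**The case against.** The strongest reply is that 20 does reproduce. With the printed difference of 4.5, a one-sided 5% t-test needs 19.86, so 20, and section 1.1 presents superiority of psilocybin as the main purpose of the design. On this view the protocol has only left sidedness unsaid, and sidedness can be left to a statistical analysis plan. Part of this stands: 20 cannot be called a proven miscalculation. But the protocol chose to print n, power and significance level together, and as printed they agree only under an unstated assumption. The directional statement in 1.1 is offset by the predictions of comparable and equivalent efficacy, so a one-sided test cannot be inferred. Nor can a later plan make the printed equation true, or make 20 right for a two-sided test.

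It can also be said that a one-sided origin is itself an inference. The BDI difference in the same section, 10.7 − 5.5 = 5.2, combined with the QIDS SD of 5.6 gives 19.2, so 20, two-sided. That mixes two scales and is not the calculation described, so it does not justify the 20; it does mean that how the 20 arose is not known.

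Third, the error may lie in the expression and not in the value, since 9.2 × 5.5/10.7 = 4.73 rounds to 4.7. This stands, and the correction must allow for it.

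Finally, the planned size is 30, so nothing in the design changes. This also stands, within limits. A reader might infer that the protocol claims a safety margin of 10 per condition (30 − 20) that a two-sided reading would erode. The document does not support that: it states no margin, gives no rule leading from 20 to 30, and also calls the numbers appropriate for the imaging.

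**Conclusion.** A minor point, but section 4.2.1 is wrong as written. The equation 9.2/2 = 4.7 is false. The stated 20 per condition matches 80% power at 0.05 only under an undeclared one-sided t-test, and then only for a difference of 4.5 or 4.6. Read two-sided, power at 20 is about 70–72% at those differences, 8 to 10 percentage points below the 80% stated, and 80% needs 25 or 26. These results rest on the protocol's own inputs: SD 5.6 in both conditions, equal allocation and a two-sample t-test. The two-sided reading is convention; the document does not state it.

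Two stronger readings should be avoided. A reader might infer that the trial is too small because of this error. It is not shown: 30 per condition exceeds every figure above, with two-sided power of 86–88% on these inputs. A reader might equally infer from that power that 30 is enough for the primary comparison. That is not shown either. The inputs describe 25mg versus 1mg psilocybin, whereas section 4.1.2 makes the primary efficacy comparison psilocybin versus escitalopram, for which section 4.2.1 gives no assumed difference and predicts equal efficacy.

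**What to change.** In section 4.2.1:

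1. Reconcile the expression with the value. Write 4.6 if the stated 50% is meant, or 9.2 × 5.5/10.7 = 4.73 if the source ratio is meant, and state the resulting difference.
2. Declare whether the test is one- or two-sided.
3. Restate n and power to match:
   - two-sided 5%: 25 per condition at a difference of 4.6 (81.2% power), or 26 at 4.5 (81.1%) or 4.47 (80.6%);
   - explicitly one-sided 5%: 20 per condition at 4.6 (81.8%) or 4.5 (80.3%), or 21 at 4.47 (81.5%).
4. If the power at 30 per condition is quoted, say that it applies to the 25mg versus 1mg psilocybin contrast.

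The cost is a few sentences. This point gives no reason to change the planned 60 completers.

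### Protocol 1.1 and 4.2.1 predict both superior and equivalent efficacy for the week-6 QIDS contrast, and its 80% power is calculated against 1 mg psilocybin alone, without the escitalopram that condition 2 takes

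*Protocol*

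**What the plan says.** **Hypotheses.** Section 1.1 (Basic study design) gives as the main purpose a test that two doses of psilocybin "will show a superior efficacy to escitalopram and crucially, a different" mechanism of action. The next sentence reads: "Secondarily, we predict that conditions 1 and 2 will show comparable efficacy at 6 weeks but with a different side-effect profile". Section 4.2.1 (Sample size) closes with "Equivalent efficacy (primary outcome) is predicted for the escitalopram vs 25mg psilocybin conditions but with different mechanisms of action".

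**Endpoint and test.** Section 4.1.2 makes the primary efficacy contrast the QIDS change to 6 weeks after the first dosing session, psilocybin arm against escitalopram arm. Section 10 states: "The study is powered for a baseline vs week 6 t-test on the QIDS-16 (condition 1 vs condition 2"). No other efficacy test is named, and no equivalence or non-inferiority margin appears.

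**Sample size.** Section 4.2.1 starts from a pilot reduction of 9.2 points (SD 5.6). For the control arm it says: "To inform what can be expected with 1mg psilocybin, we can refer to the recent end-of-life anxiety trial". It halves the pilot effect (printed as 9.2/2 = 4.7), assumes equal variance, and concludes that "we would require 20 patients per condition to achieve the desired power of 80%, p < 0.05". It then plans 30 per condition.

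**What condition 2 receives.** Sections 1.1, 2 and 2.1.2 give condition 2 two 1 mg psilocybin sessions plus six weeks of daily escitalopram. Section 2.1.2 expects that patients starting an SSRI "would report some improvements in depressive symptoms after even this relatively brief treatment period of 6 weeks".

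**The concern.** There are two faults, and they compound each other.

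First, superiority and equivalence are both predicted for one comparison. A win for psilocybin would bear out section 1.1, and a null result could be presented as bearing out section 4.2.1. The protocol does not fix in advance which result supports its efficacy hypothesis. Because the only named test is one of difference and there is no margin, a non-significant result would not establish equivalence.

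Second, the control assumption leaves out the active comparator. Section 10 presents the power as power for condition 1 versus condition 2, so a reader will take it as power against escitalopram. The calculation instead describes 25 mg psilocybin against 1 mg psilocybin, and the trial has no arm that receives 1 mg alone. Section 4.2.1 also sizes the trial for a gap of about 4.6 points while predicting, in the same section, no gap between the same two arms.

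**Working it through.** **Inputs (section 4.2.1).** Reduction on 25 mg: 9.2. Assumed reduction on 1 mg: 9.2/2 = 4.6 (printed 4.7). Difference: 9.2 − 4.6 = 4.6, or 9.2 − 4.7 = 4.5 with the printed value. SD 5.6 in both arms, alpha 0.05 with sidedness not stated, 1:1 allocation. All power figures use the two-sample t-test (noncentral t).

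**Step 1: reproduce 20 per condition.**

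| Difference | n per arm for 80%, one-sided | n per arm for 80%, two-sided | Two-sided power at 20 per arm |
|---|---|---|---|
| 4.6 | 20 (power 0.818) | 25 (0.812) | 0.716 |
| 4.5 | 20 (power 0.803) | 26 (0.811) | 0.697 |

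The figure of 20 reproduces only with one-sided alpha 0.05.

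**Step 2: precision at 30 per arm.** SE = 5.6 × √(2/30) = 1.446. With 58 df, t(0.975) = 2.002, so the 95% CI half-width is 2.002 × 1.446 = 2.9 points.

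**Step 3: how much escitalopram effect the design tolerates.** The smallest true difference with 80% power at 30 per arm is 4.12 points two-sided, or 3.64 one-sided. Holding psilocybin at 9.2, condition 2 may improve by at most:
- two-sided: 9.2 − 4.12 = 5.08, which is 5.08 − 4.6 = 0.48 above the 1 mg assumption;
- one-sided: 9.2 − 3.64 = 5.56, which is 5.56 − 4.6 = 0.96 above it.

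If the printed 4.7 is used, the room is 0.38 and 0.86.

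**Step 4: power against escitalopram.** The protocol gives no expected QIDS change on escitalopram, so the 4-, 3- and 2-point rows are assumptions shown as a range.

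| True difference | Power at 30 per arm, two-sided | Power at 30 per arm, one-sided | n per arm for 80%, two-sided / one-sided |
|---|---|---|---|
| 4.6 (1 mg alone) | 88% | 93% | 25 / 20 |
| 4 (assumed) | 78% | 86% | 32 / 25 |
| 3 (assumed) | 53% | 66% | 56 / 44 |
| 2 (assumed) | 27% | 39% | 125 / 98 |
| 0 (equivalence prediction) | 5% | 5% | – |

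**Step 5: would 30 per arm support equivalence?** That depends on a margin the protocol does not give. With two one-sided tests at 5%, truly equal arms and 1,000,000 simulated trials, equivalence is shown in 87% of trials at an assumed margin of 4.6, 72% at 4, 32% at 3 and 0.2% at 2.

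**The case against.** The strongest reply has four parts.

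- **Superiority is not tied to the QIDS.** The superiority sentence in 1.1 names neither the QIDS nor week 6, so the clash on that endpoint is partly an inference. It is a short one: 1.1 itself sets the efficacy endpoint at 6 weeks, and 2.2.1 and 4.1.2 make the QIDS the primary efficacy measure. Section 4.2.1 attaches equivalence to the primary outcome, so the word introducing the second prediction in 1.1 as secondary does not separate the two.
- **Equivalence may be only an expectation.** Nothing says a null t-test will be read as equivalence. That is fair, and the equivalence figures in Step 5 rest on margins chosen for illustration. The 5% in the last row of Step 4 is simply the error rate of any such test. But an expectation of no difference still contradicts a stated purpose of showing one, and it contradicts the difference used for sizing.
- **Section 4.2.1 is open about its basis.** It does say that it models 1 mg psilocybin. The misleading sentence is chiefly the one in section 10, which carries that power over to condition 1 versus condition 2.
- **Sidedness and the arithmetic slip are small.** Agreed. The trial plans 30 rather than 20 per arm, and 30 gives 86–88% two-sided power for the stated 4.5–4.6 points. The extra ten per arm do not cure the comparator problem, as Step 3 shows.

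The 9.2 is itself uncertain: the pilot was in treatment-resistant patients, whereas section 2.4.1 says this trial is not restricted to them. The 0.5- and 1.0-point tolerances are therefore conditional on 9.2 and SD 5.6.

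**Conclusion.** The concern holds and must be fixed. The protocol attaches two incompatible predictions to its primary efficacy contrast, and its power claim omits the active treatment in the control arm. The existing calculation supports a claim about 25 mg versus 1 mg psilocybin. It does not support 80% power against escitalopram unless the true difference is at least about 4.1 points (two-sided) or 3.6 (one-sided). How far power actually falls cannot be settled from the protocol, because it gives no escitalopram effect. The size of the problem rests on SD 5.6, a psilocybin change of 9.2, 30 completers per arm, and the assumed differences from escitalopram.

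**What to change.** 1. Reconcile 1.1 and 4.2.1 to one efficacy hypothesis for QIDS at week 6. Superiority matches the stated main purpose and the t-test in section 10. If the sponsor wants equivalence or non-inferiority instead, state a margin and a matching test.
2. Remove or reword the conflicting prediction, and state that a non-significant t-test will not be read as equivalence.
3. In 4.2.1 and section 10, say that the 4.6-point difference and its power refer to 1 mg psilocybin alone, state the sidedness, and correct 9.2/2 to 4.6.
4. Restate power at 30 per arm against escitalopram over a range of differences chosen by the sponsor and labelled as assumptions, such as the 4-, 3- and 2-point rows above.

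A separate minor wording point: section 2.2.1 lists the response to emotional faces among secondary imaging outcomes, while 4.1.1 makes the amygdala response to faces the primary fMRI outcome. Limiting the list in 2.2.1 to the other imaging outcomes removes the overlap.

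**Cost.** These are text changes; arms, visits and data stay as they are. The stated power becomes less favourable, falling below 80% once the assumed difference is under about 4.1 points (two-sided) or 3.6 (one-sided). The sponsor must accept that openly or justify a larger sample, which would go beyond a text change.
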